1.3. Sample Size and Power

It is expected that around 70% of the subjects in the previous core studies GLPG0634-CL-203 (N=595, approximately) and GLPG0634-CL-204 (N=280, approximately) will roll over into this study, corresponding to a sample size of roughly 600 subjects: $0.7 \times (595 \text{ subjects in study 203} + 280 \text{ subjects in study 204}) = 612$.

2. TYPE OF PLANNED ANALYSIS

2.1. Data Monitoring Committee Analyses

An external multidisciplinary Data Monitoring Committee (DMC) will review the progress of the study and perform interim reviews of safety data in order to protect subject welfare and preserve study integrity. To ensure the best interests of the participants, the DMC will recommend to the sponsor if the nature, frequency, and severity of adverse effects associated with the study treatment warrant the early termination of the study, the continuation of the study, or the continuation of the study with modifications.

The initial review has been conducted approximately 3 months after the DMC organizational meeting. The 2nd and 3rd DMC meetings have been conducted approximately 3 months after the previous meeting. Subsequent DMC meetings will be scheduled at approximately 12 months intervals following the 3rd DMC meeting.

The DMC's role and responsibilities and the scope of analysis to be provided to the DMC are provided in a mutually agreed upon charter, which defines the DMC membership, meeting logistics, and meeting frequency.

2.2. Pharmacovigilance & Epidemiology (PVE) Analysis

The Pharmacovigilance & Epidemiology (PVE) analysis may be conducted periodically as needed in order to review emerging safety data from GLPG0634-CL-205.

2.3. Interim Analysis for Conference

A subset of efficacy and safety data may be analyzed periodically as needed for the purpose of possible publication.

2.4. Week 156 Analysis

A planned Week 156 analysis will be conducted after all subjects have either completed their Week 156 visit or prematurely discontinued from the study.

2.5. Final Analysis

After all subjects have completed the study, outstanding data queries have been resolved or adjudicated as unresolvable, and the data have been cleaned, the final analysis of the data will be performed.

3. GENERAL CONSIDERATIONS FOR DATA ANALYSES

Analysis results will be presented using descriptive statistics. For categorical variables, the number and percentage of subjects in each category will be presented; for continuous variables, the number of subjects (n), mean, standard deviation (SD) or standard error (SE), median, first quartile (Q1), third quartile (Q3), minimum, and maximum will be presented.

By-subject listings will be presented for all subjects in the Safety Analysis Set and sorted by subject identification (ID) number, visit date, and time (if applicable). Data collected on log forms, such as AEs, will be presented in chronological order within the subject. The treatment group to which subjects were randomized or assigned will be used in the listings, as well as age, sex at birth, race, and ethnicity.

3.1. Analysis Sets

Analysis sets define the subjects to be included in an analysis. Analysis sets and their definitions are provided in this section. The analysis set will be identified and included as a subtitle of each TFL.

For each analysis set, the number and percentage of subjects eligible for inclusion, as well as the number and percentage of subjects who were excluded and the reasons for their exclusion, will be summarized by treatment group.

3.1.1. Full Analysis Set

The Full Analysis Set (FAS) includes all subjects who enrolled in GLPG0634-CL-205 and received at least one dose of study drug in GLPG0634-CL-205. This is the primary analysis set for efficacy analyses.

The study drug in GLPG0634-CL-205 is filgotinib. The study drugs in the core studies are filgotinib and placebo to match (PTM).

3.1.2. Safety Analysis Set

The Safety Analysis Set includes all subjects who enrolled in GLPG0634-CL-205 and received at least one dose of study drug in GLPG0634-CL-205. This is the primary analysis set for safety analyses.

3.2. Subject Grouping

For analyses based on the FAS subjects will be grouped according to the treatment to which they were randomized or assigned in GLPG0634-CL-205. For analyses based on the Safety Analysis Set, subjects will be grouped according to actual treatment received in GLPG0634-CL-205. The actual treatment received will differ from the randomized treatment only when their actual treatment differs from randomized treatment for the entire GLPG0634-CL-205 treatment duration.

Subjects will be presented by the following groups:

- Filgotinib with MTX
- Filgotinib monotherapy

The filgotinib with MTX group includes subjects who were from GLPG0634-CL-203 and randomized or assigned to filgotinib 100 mg q.d., filgotinib 100 mg b.i.d. or filgotinib 200 mg q.d. in GLPG0634-CL-205. The filgotinib monotherapy group includes subjects who were from GLPG0634-CL-204 and randomized or assigned to filgotinib 100 mg q.d., filgotinib 100 mg b.i.d. or filgotinib 200 mg q.d. in GLPG0634-CL-205.

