 - Subjects with persistent abnormal laboratory values associated with the use of the study medication (including but not limited to hematology, liver and renal function values) during one of the 2 core studies (GLPG0634-CL-203 or GLPG0634-CL-204), according to the investigator's clinical judgment.
 - Subjects with diagnosis since the inclusion to GLPG0634-CL-203 or GLPG0634-CL-204 core studies of rheumatic autoimmune disease or inflammatory joint disease other than RA, except for secondary Sjögren's syndrome.
- Primary Endpoint:** Safety and tolerability of long-term dosing of filgotinib 200 mg q.d. and 100 mg b.i.d.

- Secondary Endpoints:** Evolution in the percentage of subjects achieving American College of Rheumatology (ACR)20, ACR50, ACR70, and ACR-N responses; European League Against Rheumatism (EULAR) responses; ACR/EULAR remission, clinical disease activity index (CDAI), simplified disease activity index (SDAI), and the disease-activity score based on 28 joints (DAS28 c-reactive protein [CRP]) every 12 weeks or until the Final Visit or the Early Discontinuation Visit (EDV). Change from Baseline in the Quality of Life (functional assessment of chronic illness therapy [FACIT] fatigue scale and 36-item short form health survey [SF-36] scores) every 48 weeks or until the Final Visit or the EDV.
- Safety Analysis:** The safety analysis will be performed for all subjects who used the study medication at least once in this study. Assessment of treatment-emergent adverse events, and of changes from Baseline in laboratory parameters, vital signs, physical examination, and electrocardiograms.
- Efficacy Analysis:** ACR20, ACR50, ACR70, ACR-N, EULAR response, and ACR/EULAR remission, DAS28(CRP), components of the ACR, and DAS28, CDAI, SDAI, and Quality of Life data (FACIT fatigue scale and SF-36 questionnaire) at each post dosing visit (as appropriate) will be analyzed descriptively. Changes from Baseline will be examined to check for evolution over time in treatment effect.

4 Table of Contents

1	Protocol Approval Signatures	2
2	Study Personnel	3
3	Synopsis	4
4	Table of Contents	7
	LIST OF TABLES	9
5	List of Abbreviations and Definition of Terms	10
6	Introduction	12
6.1	Rheumatoid Arthritis	12
6.2	Background on Filgotinib	13
6.3	Background - Pre-clinical Studies	13
6.3.1	Physical, Chemical and Pharmaceutical Properties and Formulations	13
6.3.2	Nonclinical Pharmacology	14
6.3.2.1	Primary and Secondary Pharmacology	14
6.3.2.2	Safety Pharmacology	14

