6.4. Analysis of the Efficacy Endpoint

For binary efficacy endpoints both OC and NRI data will be summarized using descriptive statistics (counts and proportions of subjects) by treatment and visit. For continuous efficacy endpoints, OC data will be summarized using descriptive statistics (sample size, mean, SD, median, Q1, Q3, minimum and maximum) by treatment and visit. No formal statistical testing is planned.

Plots of proportions of subjects for categorical endpoints and mean \pm SD for continuous endpoints will be presented over time by treatment and by visit.

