7.1.6.1. Summaries of AE incidence in Combined Severity Grade Subsets

The number and percentage of subjects who experienced at least 1 TEAE will be provided and summarized by SOC, HLT, PT, and treatment group. For other AEs described below, summaries will be provided by SOC, PT, and treatment group:

- TEAEs of Grade severe
- TEAEs of Grade moderate or higher
- All TE treatment-related AEs
- TE Treatment-related AEs of Grade severe
- TE Treatment-related AEs of Grade moderate or higher
- All TE SAEs
- All TE treatment-related SAEs
- All TEAEs leading to premature discontinuation of any study drug
- All TEAEs leading to premature discontinuation of study
- All TEAEs leading to temporary interruption of any study drug
- All TE SAEs leading to death (ie, outcome of death)

A brief, high-level summary of AEs described above will be provided by treatment group and by the number and percentage of subjects who experienced the above AEs. All deaths reported in the study will be also included in this summary.

Multiple events will be counted only once per subject in each summary. Adverse events will be summarized and listed first in alphabetic order of SOC and HLT within each SOC (if applicable), and then by PT in descending order of total frequency within each SOC. For summaries by

severity grade, the most severe grade will be used for those AEs that occurred more than once in an individual subject during the study.

In addition to the above summary tables, all TEAEs and TE treatment-related AEs will be summarized by PT only, in descending order of total frequency.

In addition, data listings will be provided for the following:

- All AEs, indicating whether the event is treatment emergent
- All AEs of Grade severe
- All AEs of Grade moderate or higher
- SAEs
- Deaths
- All SAEs leading to death (ie, outcome of death)
- AEs leading to premature discontinuation of any study drug
- AEs leading to premature discontinuation of study
- AEs leading to temporary interruption of any study drug

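### SAP 3.2 sets a rule by assigned or actual treatment but presents two columns by core study, so no pre-specified summary separates 200 mg q.d. from 100 mg b.i.d. among CL-203 subjects

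*SAP*

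**What the plan says.** SAP 3.2 opens with a rule for each analysis set. For efficacy: "For analyses based on the FAS subjects will be grouped according to the treatment to which they were randomized or assigned in GLPG0634-CL-205". For the Safety Analysis Set, "subjects will be grouped according to actual treatment received in GLPG0634-CL-205", where actual treatment counts as different only if it differed throughout CL-205.

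The same section then names the groups to be presented, and there are two. The first is *filgotinib with MTX*: "The filgotinib with MTX group includes subjects who were from GLPG0634-CL-203 and randomized or assigned to filgotinib 100 mg q.d., filgotinib 100 mg b.i.d", or 200 mg q.d. The second is *filgotinib monotherapy*: "The filgotinib monotherapy group includes subjects who were from GLPG0634-CL-204", with the same three regimens merged.

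Later sections rely on these groups. For binary efficacy endpoints (SAP 6.4), "both OC and NRI data will be summarized using descriptive statistics (counts and proportions of subjects) by treatment and visit". Subjects with treatment-emergent adverse events (TEAEs) (SAP 7.1.6.1) "will be provided and summarized by SOC, HLT, PT, and treatment group". Neither section defines other columns. Regimen appears only at subject level (SAP 3): "The treatment group to which subjects were randomized or assigned will be used in the listings".

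The primary endpoint in the protocol synopsis reads: "Safety and tolerability of long-term dosing of filgotinib 200 mg q.d. and 100 mg b.i.d". Protocol 6.7 gives the collection of long-term data on both dosing frequencies as the reason for leaving subjects on the frequency they had in the core study.

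**The concern.** The two halves of SAP 3.2 do not fit together. A rule that distinguishes assigned from actual treatment matters only if a change of treatment can change a subject's column. Here the column depends only on the core study the subject came from.

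What is at stake is how directly the report answers its own primary question. The endpoint names two regimens, and the planned tables summarise neither alone for CL-203, the only core study that feeds both. A programmer who follows the explicit list would produce pooled tables, and a reader who wanted the safety profile of 100 mg b.i.d. would have to rebuild it from listings.

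The second issue is the label. CL-204 subjects may start MTX in this study at the investigator's judgment (protocol 8.1, SAP 1.2), and no SAP rule moves or splits them. Events under the *monotherapy* header can therefore have occurred on filgotinib plus MTX.

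**Working it through.** **Does the opening rule have any effect?** Take a CL-203 subject assigned 100 mg b.i.d. who received 200 mg q.d. throughout CL-205. Assigned grouping puts this subject in *filgotinib with MTX*; actual grouping does the same. The result is identical for every pair of the three regimens and in both columns. The rule cannot alter any summary.

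**Where does the pooling matter?** In the design table, every CL-204 arm rolls over to 200 mg q.d., so the b.i.d. category in the *monotherapy* definition should be empty. The regimen issue is confined to the CL-203 column.

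**How large are the groups?** The plan's own sample-size figure is 0.7 × (595 + 280) = 612.5, printed as 612. Actual enrolment was 739 (protocol 8.3.1), so I use that with the arm sizes in protocol Tables 6-1 and 6-2.

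- CL-203: 86 + 82 + 85 + 86 + 86 + 85 + 84 = 594. CL-204: 72 + 72 + 70 + 69 = 283. Total 877.
- The design table splits the 86 CL-203 placebo subjects evenly between frequencies, 43 to each.
- q.d. = 82 + 85 + 86 + 43 = 296. b.i.d. = 86 + 85 + 84 + 43 = 298, which is 298/594 = 50.2% of CL-203.
- Assuming equal rollover across arms, 739/877 = 0.843. This gives about 249 q.d., 251 b.i.d. and 238 from CL-204.
- Bounds without that assumption about the two studies: the CL-203 column holds at least 739 − 283 = 456 and at most 594. Keeping the 296:298 split, the smaller regimen at the lower bound is 456 × 296/594 = 227, and the larger at the upper bound is 298.
- SAP 1.2 says US males were limited to 100 mg q.d. Their number is not given, so the regimen counts are slightly too high by an unknown amount.

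**What can a pooled column hide?** For illustration, 15 events in 500 subjects is 3%. Five in 250 and ten in 250 (2% and 4%), or the reverse, give the same pooled entry. This shows only that the column cannot tell these cases apart; it is not evidence that they differ.

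**What precision would regimen columns have?** The 95% half-width is 1.96 × √(p(1 − p)/n), with p = 0.05 assumed:

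| Column | n | Half-width (points) |
|---|---|---|
| One regimen | 250 | 2.7 |
| One regimen, bounds | 227; 298 | 2.8; 2.5 |
| Pooled CL-203 | 500 | 1.9 |
| Pooled CL-203, bounds | 456; 594 | 2.0; 1.8 |

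**MTX in the CL-204 column.** The number who start MTX is not given. Each 10% would be about 0.10 × 238 = 24 subjects.

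**The case against.** **Pooling is consistent with the objective.** The primary objective (protocol 7.1, SAP 1.1) concerns filgotinib as such, and protocol 6.6 describes one stable 200 mg daily dose given either way. The endpoint names both regimens but does not ask for separate tables. This stands: a reader might infer a breach of the protocol, and the documents do not support that. It is a reason to keep the pooled totals. It does not make the opening rule work, and it does not serve the purpose stated in protocol 6.7.

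**Optional analyses could fill the gap.** Protocol 8.9.1.1 allows other subgroups, 8.9.1.3 further safety subgroups, and 8.9.1.4 exploratory efficacy analyses. So one cannot say that the report will never show the regimens, only that none of its planned summaries does. The one dose-based example, a division by mean actual dose, would not separate 200 mg q.d. from 100 mg b.i.d., since both are 200 mg a day.

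**No regimen difference has been seen.** Protocol 6.4 reports no difference in overall TEAE incidence across the CL-203 dosing groups. This is the most direct safety text, and it argues against alarm. But it covers 24 weeks, and no rates are given by regimen, so it does not settle long-term safety. Conversely, a reader might take the numerically higher ACR responses on b.i.d. at 200 mg/day in Table 6-1 as a sign that the regimens differ. They are not: at Week 12, ACR20 was 78.6% against 68.6% at that dose, but 60.0% against 63.5% at 100 mg/day, and efficacy says nothing about safety.

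**The MTX label is defined and partly reported.** SAP 3.2 states who is in each column, the labels echo the core-study descriptions, and SAP 7.4 counts MTX users by group. The protocol's split by MTX background is optional. What remains is an inaccurate header and no summary of when MTX was started.

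**Document versions.** The SAP was written against protocol Amendment 3, and the protocol to hand is Amendment 4. The change entries that can be read do not touch the endpoint or the regimens.

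**Conclusion.** The point holds and is minor. The assigned/actual rule in SAP 3.2 has no effect on any summary, and no pre-specified summary separates the two named regimens among CL-203 subjects. About half of that column is b.i.d., on the assumption of equal rollover and before removing subjects assigned 100 mg q.d. The *monotherapy* header is inaccurate for any CL-204 subject who starts MTX.

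All analyses are descriptive, so no error rate, power or decision rule is involved. Nothing here shows that the regimens differ in safety, or that they are the same. Nor should one infer that showing regimens costs precision: if the pooled totals stay, the pooled estimate is unchanged. The ±2.7 points for a single regimen rests on an assumed 5% event rate.

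**What to change.** (a) In SAP 3.2, for the safety and main efficacy summaries, add columns for CL-203 200 mg q.d., CL-203 100 mg b.i.d., CL-204 200 mg q.d., and subjects assigned 100 mg q.d. Keep the pooled totals. State that the assigned/actual rule applies to these columns.

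(b) Footnote what the columns contain. They show the starting regimen. TEAEs count from the first filgotinib dose in the core study (SAP 7.1.5.1), so they may include time on lower core doses. Subjects reduced to 100 mg q.d. during CL-205 (protocol 8.6.6) stay in their starting column, because of the entire-duration condition in SAP 3.2. Report how many were reduced in each column.

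(c) Relabel the two pooled groups by core study, for example 'from CL-204, started as monotherapy', and add the timing of MTX starts to the count that SAP 7.4 already provides.

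The cost is SAP wording and longer tables. Assigned treatment and medication dates are already collected.

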3.3. Missing Data and Outliers

3.3.1. Missing Data

In general, missing data will not be imputed unless methods for handling missing data are specified. Exceptions are presented in this document.

For missing last dosing date of study drug, imputation rules are described in Section 4.2. For partial date of initial RA diagnosis, imputation rules are described in Section 5.2. The handling of missing or incomplete dates for AE onset is described in Section 7.1.5.2. The handling of missing or incomplete dates for prior medications is described in Section 5.2. and for concomitant medications in Section 7.4. Imputation rules adopted in the efficacy analyses are specified in Section 6.1.

3.3.2. Outliers

Outliers will be identified during the data management and data analysis process, but no sensitivity analyses will be conducted. All data will be included in the data analyses.

3.4. Data Handling Conventions and Transformations

In general, age (in years) on the date of the first dose of study drug in the core studies will be used for analyses and presentation in listings. If an enrolled subject was not dosed with any study drug in the core studies, the randomization date will be used instead of the first dosing date of study drug. For the screen failures in the core studies, the date the last informed consent was signed in the core studies will be used for age calculation. If only birth year is collected on the CRF, “01 July” will be used for the unknown birth day and month for the purpose of age calculation.

Non-PK Data that are continuous in nature but are less than the lower limit of quantitation (LOQ) or above the upper LOQ will be imputed as follows:

- A value that is 1 unit less than the LOQ will be used to calculate descriptive statistics if the datum is reported in the form of “< x” (where x is considered the LOQ). For example, if the values are reported as < 50 and < 5.0, values of 49 and 4.9, respectively, will be used to

calculate summary statistics. An exception to this rule is any value reported as < 1 or < 0.1 , etc. For values reported as < 1 or < 0.1 , a value of 0.9 or 0.09, respectively, will be used for calculate summary statistics.

- A value that is 1 unit above the LOQ will be used to calculate descriptive statistics if the datum is reported in the form of “ $> x$ ” (where x is considered the LOQ). Values with decimal points will follow the same logic as above.
- The LOQ will be used to calculate descriptive statistics if the datum is reported in the form of “ $\leq x$ ” or “ $\geq x$ ” (where x is considered the LOQ).

3.5. Analysis Visit Window

3.5.1. Definition of Study Day

The first dose date of individual study drug will be calculated separately for each study drug in a treatment group. Study Day 1 is defined as the first dose date of any study drug, which is the minimum of the first dose dates of individual study drugs in a treatment group.

The last dose date of individual study drug will be calculated separately for each study drug in a treatment group. The last dose date of any study drug will be defined as the maximum of the last dose dates of individual study drugs in a treatment group.

The first dose date of individual study drug in GLPG0634-CL-205 is identified by the first drug dispense date + 1 day. The last dose date of individual study drug in GLPG0634-CL-205 is identified by the Final Visit date or the Early Discontinuation Visit date.

Study Day will be calculated from the Reference Date and derived as follows:

- For postdose study days: Assessment date – Reference Date + 1
- For days prior to the first dose: Assessment date – Reference Date

Reference Date is defined as follows:

- For efficacy data in the core studies: Study Day 1 in the core studies
- For efficacy data in GLPG0634-CL-205: Study Day 1 in GLPG0634-CL-205
- For safety data: The first dose date of filgotinib in the core studies or GLPG0634-CL-205

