8.6.9 Treatment Compliance and Drug Accountability

The investigator or designated study personnel will maintain a log of all drug dispensed and returned. Drug supplies for each subject will be inventoried and accounted for throughout the study.

Subjects with a poor compliance (<80% or >120%) will be retrained by the study site. If study drug compliance remains <80% or >120% between study visits, or if the subject missed more than 2 visits, the subject will be evaluated for potential discontinuation. Any discontinuation should be done in consultation with the *medical monitor*.

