Week 72	505	464	547
Week 84	589	548	631
Week W	7xW+1	7xW-40	7xW+43

CRP measured on or after nominal follow up visit will not be assigned analysis window and summarized, but will be included in the listing.

Vital signs, ECG, and safety laboratory data collected in the follow up period will also be summarized. The analysis window for the post-treatment follow-up period is defined as from (last dose date of filgotinib + 1 day) to (last dose date of filgotinib + 30 days). If multiple valid, nonmissing measurements exist in the post treatment follow-up visit window, the latest record will be selected for analysis. If the chronological order cannot be determined, for any given subject, the value with the worst severity will be selected for categorical variable, and the average will be taken for continuous variable. Data obtained after last dose date plus 30 days will be excluded from the summaries, but will be included in the listings.

3.5.3. Selection of Non-Efficacy Data in the Event of Multiple Records in an Analysis Visit Window

Depending on the statistical analysis method, single values may be required for each analysis window. For example, change from baseline by visit usually requires a single value, whereas a time-to-event analysis would not require 1 value per analysis window.

If multiple valid, nonmissing, continuous measurements exist in an analysis window, records will be chosen based on the following rules if a single value is needed:

- In general, the filgotinib baseline value will be the last nonmissing value on or prior to the first dose date of filgotinib in the core studies or GLPG0634-CL-205, unless otherwise specified. If multiple measurements occur on the same day, the last nonmissing value prior to the time of first dose of filgotinib in the core studies or GLPG0634-CL-205 will be considered as the filgotinib baseline value. If these multiple measurements occur at the same time or the time is not available, the average of these measurements (for continuous data) will be considered the filgotinib baseline value.
- For postbaseline visits:
 - The record closest to the nominal day for that visit will be selected.
 - If there are 2 records that are equidistant from the nominal day, the later record will be selected.
 - If there is more than 1 record on the selected day, the average will be taken, unless otherwise specified.

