4.2. Extent of Filgotinib Exposure

Total duration of exposure to filgotinib will be defined as (last dose date of filgotinib in GLPG0634-CL-205 - first dose date of filgotinib in the core studies or GLPG0634-CL-205 + 1), regardless of any temporary interruptions in administration and will be expressed in weeks using up to 1 decimal place (eg, 4.5 weeks).

If the last filgotinib dosing date is missing, the latest date among the clinical visit date and laboratory sample collection date that occurred during the on-treatment period will be used.

If subjects are continuing on study drug, The data cutoff date will be used to impute the last dosing date for the calculation of the duration of exposure to filgotinib.

The total duration of exposure to filgotinib will be summarized using descriptive statistics and using the number (ie, cumulative counts) and percentage of subjects exposed for filgotinib baseline and every 12 weeks afterwards.

Summaries will be provided by treatment group for the Safety Analysis Set. No formal statistical testing is planned.

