7.1.5. Treatment-Emergent Adverse Events

7.1.5.1. Definition of Treatment-Emergent Adverse Events

Treatment-emergent adverse events (TEAEs) are defined as any AEs with an onset date on or after the filgotinib start date in the core studies or GLPG0634-CL-205, and no later than 30 days after permanent discontinuation of filgotinib in GLPG0634-CL-205.

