7.1.5.2. Incomplete Dates

If the onset date of the AE is incomplete and the AE stop date is not prior to the first dosing date of filgotinib in the core studies or GLPG0634-CL-205, then the month and year (or year alone if month is not recorded) of onset determine whether an AE is treatment emergent. The event is considered treatment emergent if both of the following 2 criteria are met:

- The AE onset is the same as or after the month and year (or year) of the first dosing date of filgotinib in the core studies or GLPG0634-CL-205, and
- The AE onset date is the same as or before the month and year (or year) of the date corresponding to 30 days after the date of the last dose of filgotinib in GLPG0634-CL-205

An AE with completely missing onset and stop dates, or with the onset date missing and a stop date later than the first dosing date of filgotinib in the core studies or GLPG0634-CL-205, will be considered to be treatment emergent. In addition, an AE with the onset date missing and incomplete stop date with the same or later month and year (or year alone if month is not recorded) as the first dosing date of filgotinib in the core studies or GLPG0634-CL-205 will be considered treatment emergent.

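### SAP 3.5.1 dates the last dose of early discontinuers by the EDV, so off-drug days count as exposure and off-drug EDV values enter by-visit safety windows

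*SAP*

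**What the plan says.** For CL-205, SAP 3.5.1 gives one rule for the end of dosing: "The last dose date of individual study drug in GLPG0634-CL-205 is identified by the Final Visit date or the Early Discontinuation Visit date". It gives no priority to an actual stop date. The same section takes the first dose as the day after first dispensing.

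The date is then used in several places:

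- **By-visit windows (SAP 3.5.2).** Windows for non-efficacy data apply up to the last dose date.
- **Post-treatment window (SAP 3.5.2).** "The analysis window for the post-treatment follow-up period is defined as from (last dose date of filgotinib + 1 day"), and it closes 30 days after last dose. Later data are listed but not summarised.
- **Exposure (SAP 4.2).** Last dose minus first dose plus one day, "regardless of any temporary interruptions in administration". A fallback reads "If the last filgotinib dosing date is missing, the latest date among the clinical visit date and laboratory sample collection date", limited to dates within an on-treatment period that the SAP does not define.
- **TEAEs.** SAP 7.1.5.1 accepts onset "no later than 30 days after permanent discontinuation of filgotinib in GLPG0634-CL-205". SAP 7.1.5.2, for incomplete dates, uses "30 days after the date of the last dose of filgotinib in GLPG0634-CL-205".
- **Laboratory and concomitant medication (SAP 7.2, 7.4).** Laboratory summaries run to last dose plus 30 days; the concomitant-medication window ends at the last dosing date.

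Protocol 8.1 says an EDV will be scheduled on early withdrawal, without a time limit. Protocol 8.4.2 only encourages withdrawing subjects to complete the final evaluations. Protocol 8.6.9 says "The investigator or designated study personnel will maintain a log of all drug dispensed and returned".

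**The concern.** Protocol 8.4.2 lists many reasons for permanent discontinuation that can arise between quarterly visits, such as infection, toxicity or confirmed laboratory abnormalities. Protocol 8.4.1 allows visits to continue during an interruption, so an interruption that becomes permanent lengthens the gap. In these subjects the true last dose comes before the EDV, but the SAP treats the two as the same day.

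Long-term safety is the primary objective. The misdating falls on those who stopped early, many of them because of a safety problem. An EDV value that has begun to recover off drug can be summarised at a visit as if it were on drug. SAP 3.5.3 picks the record closest to the nominal day, so that value can also displace an on-drug value in the same window. A medication started after stopping but before the EDV is tabulated as concomitant with filgotinib.

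**Working it through.** The plan states no figure to reproduce; the check is date arithmetic.

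**Inputs**

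- *g*, days from true last dose to EDV: not given, so an assumption, shown as a range.
- *f*, days from EDV to Follow-up Visit: 2 weeks ± 4 days (Protocol 8.7.3), so 10, 14 or 18.
- End of AE recording: final Follow-up Visit (Protocol 8.8.1.2.1.2).
- TEAE and post-treatment cut-off: 30 days (SAP 7.1.5 and 3.5.2).
- Enrolled: 739 (Protocol 8.3.1).
- Share stopping early and mean exposure: assumptions.

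**1. Where EDV laboratory, vital-sign and ECG values go**

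| g | Under 3.5.1 | Under true last dose |
|---|---|---|
| 0 | by-visit window | by-visit window |
| 1 to 30 days | by-visit window | post-treatment window |
| over 30 days | by-visit window | listing only |

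A one-day gap is enough to change the placement.

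**2. TEAEs.** Suppose the SAP 7.1.5.1 cut-off is taken from the 3.5.1 date. The days of AE collection that count as treatment-emergent only because of the visit date are max(0, min(g + 30, g + f) − 30). Since f is below 30, this is max(0, g + f − 30).

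| g (days) | f = 10 | f = 14 | f = 18 |
|---|---|---|---|
| 7 | 0 | 0 | 0 |
| 14 | 0 | 0 | 2 |
| 28 | 8 | 12 | 16 |
| 42 | 22 | 26 | 30 |
| 84 | 64 | 68 | 72 |

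The count can change only when g exceeds 30 − f, which is 20, 16 or 12 days. For an illustrative gap of 13 weeks (91 days), recording stops at 91 + 18 = 109 days after true last dose at the latest.

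**3. Exposure.** Relative overstatement = share stopping early × gap ÷ mean exposure.

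- Low: 30% stop early, gap 2 weeks, mean 4 years: 0.3 × 2 / 52.18 / 4 = 0.29%.
- High: 50% stop early, gap 12 weeks, mean 2 years: 0.5 × 12 / 52.18 / 2 = 5.75%.

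Wider assumptions (20% to 50% stopping, gap 14 to 84 days, mean 1 to 5 years) give 0.2 × 14 / 365.25 / 5 = 0.15% up to 0.5 × 84 / 365.25 / 1 = 11.5%. In person-years the excess is 739 × 0.2 × 14 / 365.25 = 5.7 up to 739 × 0.5 × 84 / 365.25 = 85.0. The upper percentage needs a mean exposure of only one year. SAP 4.2 tabulates exposure every 12 weeks, so an 84-day gap can move a subject one full step.

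**The case against.** The case for leaving the rule alone has several parts.

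- **No contradiction with SAP 4.2.** A reader might infer that the missing-date rule proves an actual dosing date is collected and that 3.5.1 overrides it. The documents do not support that. Some withdrawing subjects may have no EDV, and 4.2 can be read as the fallback for them. This stands. What remains is that 4.2 depends on an undefined on-treatment period, whose end itself needs a last dose date.
- **The date may not exist.** Taking first dose from dispensing fits an eCRF without intake dates. The eCRF is not among the documents, and a dispensing log does not by itself give a last intake date. This stands, and it makes the fix conditional.
- **Adverse events.** A reader might infer that TEAEs are captured to 30 + 91 = 121 days after true last dose. They are not, because AE recording ends at the Follow-up Visit. The SAP also has no separate on-treatment AE category, and 7.1.5.1 refers to permanent discontinuation without naming the 3.5.1 date.
- **Masking.** A reader might infer that recovered EDV values hide toxicity. Graded, marked and liver summaries take the worst postbaseline value, so a later recovery cannot hide an earlier abnormality. The masking risk is confined to by-visit summaries.
- **Long gaps are not the norm.** Nothing makes the EDV wait for a quarterly visit. The laboratory stopping criteria call for a retest visit within 3 to 5 days, or 7 to 14 days for creatinine. So 13 weeks is an illustration, not an expectation.
- **The present rule is more inclusive.** This is true, and for safety it has some merit. It does not justify summarising off-drug measurements in windows meant to end at last dose; the 30-day extension already provides inclusiveness.

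**Conclusion.** The point holds for early discontinuers. As written, 3.5.1 adds off-drug days to their exposure and places off-drug EDV laboratory, vital-sign and ECG values in by-visit windows whenever the gap is at least one day. The 30-day cut-offs tied to last dose and the SAP 7.4 window shift by the gap.

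The size is limited. Exposure is overstated by about 0.3% to 5.8% under the main assumptions. This mostly touches the duration summary, because the SAP plans counts and percentages and Protocol 8.9.1.3 makes patient-year analysis optional. TEAE counts move only for gaps beyond 12 to 20 days. Completers return remaining drug at the Final Visit, so that date should lie close to their last intake. The distribution of gaps and the number of early discontinuers are not in the documents, so the actual effect cannot be fixed from them.

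This is a derivation rule that gives a wrong date for an identifiable group. It should be corrected, but it does not undermine the safety analysis as a whole.

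**What to change.** In SAP 3.5.1, for early discontinuers, define the last dose date in this order:

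1. the recorded date of last filgotinib intake or of permanent discontinuation, where one is available;
2. otherwise the EDV date;
3. if there is no EDV, the SAP 4.2 rule, with the on-treatment period defined without reference to the last dose date.

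Keep the Final Visit date for completers. Use this one date in SAP 3.5, 4.2, 7.1.5.1, 7.1.5.2, 7.2 and 7.4, and have 7.1.5.1 and 7.1.5.2 name the same anchor.

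The cost is a few sentences and one derivation, with three side effects to state in the SAP. EDV data move to the listings when the gap exceeds 30 days, and Follow-up data when it exceeds 12 to 20 days. When both fall in the post-treatment window, 3.5.2 selects the later record, so the EDV value is no longer summarised by visit. Dates rebuilt from accountability records are noisier than visit dates, so the source used for each subject should be flagged.
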